#### **10.3.5.3 Laboratory variables**

All laboratory data transferred are taken into account regardless of whether they correspond to scheduled (per protocol) or unscheduled assessments. All recorded assessments will be assigned to the most appropriate visit time points according to the best fitting time-window for that assessment using the usual location and scale summary statistics.

For each laboratory variable, the number and percentage of participants with at least one treatment-emergent marked abnormality will be summarized up to EOT + 3 days.

The change in selected laboratory values and the change in TSH will also be summarized over time up to EOT + 3 days, using the same descriptive statistics for continuous variables.

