2. ANALYSIS DETAILS

2.1. Analysis Sets

- **Screened Analysis Set:** Screened analysis set includes all participants who are screened and have a participant identification number.
- **Full Analysis Set:** Full analysis set includes all enrolled participants who were eligible to receive the study drug.
- **Safety Analysis Set:** Safety analysis set includes all participants included in Full Analysis Set who receive at least one dose of the study drug. Since all enrolled participants received at least one dose of study drug, the Full Analysis Set and Safety Analysis Set are the same in this study. For simplicity, the Safety Analysis Set will be used for all safety and efficacy analyses.
- **Pharmacokinetic Analysis Set (PKS):** PK analysis set comprises all participants included in the Safety Analysis Set who complied with the protocol sufficiently and did not deviate from the protocol in a way that might affect the PK outcome of the study. Criteria for sufficient compliance include exposure to treatment, availability of PK measurements, and absence of major protocol deviations that have an impact on the PK. Further details are provided in the PK and modeling analysis plan.

For all analyses, except the time to disease progression event, only the scheduled visits data will be used in summary outputs; both the scheduled and unscheduled visits data will be included in the listings.

The analysis set usage is summarized as following:

Table 2: Study Analysis Set Usage

	Screened Analysis Set	Full Analysis Set	Safety Analysis Set	PK Analysis Set	PK
Participant disposition	X	X	X		
Participant information (medical history, concomitant medication, contraceptives)			X		
Participant information (demographics, baseline characteristics, baseline disease characteristics)			X		
Treatment exposure, treatment discontinuation, drug accountability and compliance, protocol deviation			X		
Safety analyses			X		
Other endpoints analyses			X		
PK analyses				X	X
Efficacy exploratory analyses			X		
Sensitivity Analysis, for Efficacy exploratory analyses			X		
All listings for disposition/Recruitment	X	X	X		
All listings for Participant information	X	X	X		
All other Listings			X		

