2.4. Baseline Definition

Baseline: Baseline will be defined as the last non-missing assessment available prior to the first dose administration. Any unscheduled measurement performed before administration of study drug should also be used for determination of baseline across all the domains, as some tests may be repeated for confirmation.

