4.2. Clinical Laboratory Tests

The following laboratory parameters are evaluated:

- Hematology:
 - Hemoglobin (g/L)
 - Hematocrit (L/L)
 - Erythrocyte count ($10^9/L$)
 - Leukocyte count with differential counts ($10^9/L$)
 - Platelet count ($10^9/L$)
- Clinical chemistry:
 - Alanine aminotransferase (U/L)
 - Aspartate aminotransferase (U/L)
 - Alkaline phosphatase (U/L)
 - Total and direct bilirubin ($\mu\text{mol/L}$)
 - Creatinine ($\mu\text{mol/L}$)
 - Creatinine clearance (mL/min)
 - Serum urea nitrogen (mmol/L)
 - Uric acid ($\mu\text{mol/L}$)
 - Glucose (mmol/L)
 - Cholesterol, triglycerides (mmol/L)
 - Sodium, potassium, chloride, calcium (mmol/L)
 - Albumin (g/L)
 - NT-pro BNP (pmol/L)
 - TSH (mU/L)
 - Free T3 and free T4 (pmol/L)
 - Thyroid antibodies (U/mL)

In addition, local laboratory parameters might be available under certain circumstances and recorded in the CRF.

All recorded assessments, whether from central or local laboratory (including unscheduled) will be assigned to the most appropriate visit time points according to the best fitting time-window for that assessment

If data from a local laboratory and from the central laboratory are available for the same date, the central laboratory value will be used; if more than one valid assessment are available on the same timepoint window in the same lab, the mean value will be considered.

A laboratory test abnormality is defined as any value outside the normal range as provided by the laboratory. The direction of the abnormality (below or above the normal range) is indicated using 'H' and 'L', if applicable.

A marked (alert) laboratory test abnormality is defined as any value that fulfills the applicable condition listed in the table below for LL / HH (or LLL / HHH, respectively):

Safety parameter	Marked Abnormally Low Values		Marked Abnormally High Values	
	LL	LLL	HH	HHH
Hematology				
Hemoglobin (g/L)	< 100	< 80	Increase (> 20 g/L) above ULN or above baseline if baseline is above ULN	Increase (> 40 g/L) above ULN or above baseline if baseline is above ULN
Hematocrit (L/L)	< 0.28 F < 0.32 M	< 0.20	> 0.55 F > 0.60 M	> 0.65
Erythrocyte count (10 ⁹ /L)	NA	NA	NA	NA
Leukocyte count with differential counts (10 ⁹ /L)	< 3.0	< 2.0	> 20.0	> 100.0
Platelet count (10 ⁹ /L)	< 75	< 50	> 600	> 999
Clinical chemistry				
AST (U/L)	NA	NA	> 3 ' ULN	> 5 ' ULN
ALT (U/L)	NA	NA	> 3 ' ULN	> 5 ' ULN
Alkaline phosphatase (U/L)	NA	NA	> 2.5 ' ULN	> 5 ' ULN
Total bilirubin (µmol/L)	NA	NA	> 2 ' ULN	> 5 ' ULN

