Direct bilirubin (µmol/L)	NA	NA	> 2 ' ULN	> 5 ' ULN
Creatinine (µmol/L)	NA	NA	> 1.5 ' ULN or > 1.5 ' baseline if baseline is above ULN	> 3 ' ULN or > 3 ' baseline if baseline is above ULN
Serum urea nitrogen	NA	NA	> 2.5 x ULN	> 5 x ULN
Glucose (mmol/L)	< 3.0	< 2.2	> 8.9	> 13.9
Sodium (mmol/L)	NA	< 130	> 150	> 155
Potassium (mmol/L)	< 3.2	< 3.0	NA	> 6.0
Calcium (mmol/L)	< 2.0	< 1.75	> 2.9	> 3.1

ALT = alanine aminotransferase; AST = aspartate aminotransferase; F = female; M = male; ULN = upper limit of normal range.

Treatment-emergent marked laboratory abnormalities are defined as all marked laboratory abnormalities with onset after the study treatment start and up to EOT+3 days, that were not present at baseline or worsened during the course of the study. They will be analyzed on the Safety Analysis Set overall, by age cohort and body weight group.

For each category (i.e., LL, LLL, HH, HHH), treatment-emergent marked laboratory abnormalities are summarized for each laboratory variable overall, by age cohort and body weight group, displaying counts and percentages of participants with at least one marked treatment-emergent abnormality. Percentages are calculated by dividing the number of participants with at least one marked abnormality for the parameter under consideration by the number of participants with any post-baseline measurement.

The number of participants with laboratory abnormalities/marked abnormalities (any value outside the normal ranges for the laboratory) will be also tabulated as shift tables against baseline.

Absolute values and changes from baseline will be determined for each parameter and participant at the different timepoints of assessment and summarized overall, by age cohort and body weight group for the Safety Analysis Set. For graphs or tables with mean values, to account for changing reference ranges across age and gender, certain central and local laboratory values (Y_{ori}) and their reference ranges (LLN_{ori} , ULN_{ori}) will be normalized as Y_{norm} using a standard range (LLN , ULN) as follows:

$$Y_{norm} = LLN + \frac{(Y_{ori} - LLN_{ori})}{(ULN_{ori} - LLN_{ori})} \times (ULN - LLN)$$

If the value is negative after normalization, zero will be assigned.

The laboratory tests that require normalization and their standard ranges to be used are:

- TSH: 0.34 - 5.60 (mIU/L)
- Free T3: 4.5 - 7.8 (pmol/L)
- Free T4: 10 - 24 (pmol/L)
- Hemoglobin: 116 - 164 (g/L)
- Hematocrit: 0.34 - 0.48 (L/L)

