- Erythrocyte count: 4.1 - 5.6 ($10^{12}/L$)
- Leukocyte count: 3.80 - 10.70 ($10^9/L$)
- Neutrophil count: 1.65 - 8.15 ($10^9/L$)
- Lymphocyte count: 0.95 - 5.25 ($10^9/L$)
- Monocyte count: 0.40 - 0.90 ($10^9/L$)
- Monocyte/leukocyte: 4.0 - 7.0 (%)
- Eosinophil count: 0.00 - 0.20 ($10^9/L$)
- Eosinophil/leukocyte: 0.0 - 4.1 (%)
- Platelet count: 140 - 400 ($10^9/L$)
- Creatinine: 40 - 83 ($\mu\text{mol}/L$)
- Alkaline phosphatase: 31-110 (U/L)

- Alanine aminotransferase: 6-34 (U/L)
- Aspartate aminotransferase: 10-40 (U/L)
- Uric Acid: 137-404 ($\mu\text{mol/L}$)
- Albumin: 33 - 47 (g/L)
- Triglyceride: 0.44 - 1.40 (mmol/L)
- Cholesterol: 3.23 - 5.48 (mmol/L)

All individual laboratory data will be listed and a separate listing for participants with laboratory abnormalities will also be provided, as well as a separate listing of participants with treatment-emergent marked laboratory abnormalities.

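### SAP 2.1 restricts summaries to scheduled visits, contradicting protocol 10.3.5.3 and SAP 4.2 for laboratory data, so a marked abnormality seen only at an unscheduled test may go uncounted

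*SAP*

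**What the plan says.** The general rule is in SAP 2.1: "For all analyses, except the time to disease progression event, only the scheduled visits data will be used in summary outputs". Unscheduled results are sent to the listings. Time to disease progression is the only exception named.

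Protocol 10.3.5.3 sets a different rule for laboratory data: "All laboratory data transferred are taken into account regardless of whether they correspond to scheduled (per protocol) or unscheduled assessments". It places those results in visits "according to the best fitting time-window for that assessment using the usual location and scale summary statistics", so it covers by-visit summaries as well as the incidence count.

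SAP 4.2 follows the protocol: "All recorded assessments, whether from central or local laboratory (including unscheduled) will be assigned to the most appropriate visit time points". On incidence it says: "Treatment-emergent marked laboratory abnormalities are defined as all marked laboratory abnormalities with onset after the study treatment start and up to EOT+3 days". The percentage is formed by dividing "by the number of participants with any post-baseline measurement". SAP 4.2 also promises a listing of all individual laboratory data and one of participants with abnormalities, "as well as a separate listing of participants with treatment-emergent marked laboratory abnormalities".

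For baseline, SAP 2.4 says: "Any unscheduled measurement performed before administration of study drug should also be used for determination of baseline across all the domains".

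**The concern.** The two SAP rules cannot both be applied to laboratory data as written. Placing unscheduled values in visit windows serves little purpose if only scheduled values reach a summary. The SAP states no precedence, and its version history does not present SAP 2.1 as a departure from the protocol. Two programmers working from this SAP could produce different laboratory tables.

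The table most exposed is the incidence of treatment-emergent marked laboratory abnormalities. This is a safety endpoint in protocol 6.2, and safety is the secondary objective (protocol 2.2). Unscheduled testing is provided for: Table 5 has a laboratory entry for unscheduled visits, protocol 7.1.2 prefers central laboratory tests when PAH worsening is suspected, and protocol 7.2.4.1 routes unscheduled tests and re-tests to the central laboratory. Scheduled hematology and chemistry after baseline fall at Weeks 4, 12 and 16, then every 3 months for a year and every 6 months thereafter. Between those dates an unscheduled test may be the only laboratory look. Such tests are often done for cause, which is when a marked value is plausible.

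**Working it through.** The plan states no figure on this point, so there is nothing to reproduce. The check compares the rules and then sizes the effect of one uncounted child.

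**1. The rules side by side**

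| Item | Under SAP 2.1 | Under protocol 10.3.5.3 and SAP 4.2 |
|---|---|---|
| Unscheduled laboratory value | Listing only | Assigned to a visit window and used |
| Numerator, marked abnormalities | Scheduled values only | All with onset from treatment start to EOT + 3 days |
| Denominator | Children with a scheduled post-baseline value | Children with any post-baseline value |
| Listing of treatment-emergent marked abnormalities | Includes unscheduled values | Includes unscheduled values |

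Under SAP 2.1 the listing could show a child whom the table, built on the same definition, omits.

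**2. Which children are affected**

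The endpoint counts children with one or more events. A re-test after a marked scheduled value therefore changes nothing. Only a child whose marked value occurs solely at an unscheduled test is lost. Dropping unscheduled values can lower this count but cannot raise it.

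**3. Size per child**

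Inputs: about 20 enrolled per cohort and about 60 in total (SAP 1.2). I also show 15, the PK-evaluable minimum, as a smaller cohort; it is not the planned laboratory denominator. I assume every child has a scheduled post-baseline value, so the denominator is the same under both rules. The change in incidence is 1/n:

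- 1/20 = 5.0 percentage points
- 1/15 = 6.7 percentage points
- 1/60 = 1.7 percentage points

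Exact (Clopper-Pearson) 95% limits with that child counted and not counted:

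| n | Counted | Not counted |
|---|---|---|
| 20 | 1/20 = 5.0% (0.13 to 24.87) | 0/20 = 0% (0 to 16.84) |
| 60 | 1/60 = 1.7% (0.04 to 8.94) | 0/60 = 0% (0 to 5.96) |

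**4. By-visit means, with assumed values**

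Take one child with two central potassium values in one window: 6.4 mmol/L unscheduled and 5.5 mmol/L scheduled.

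- SAP 2.1: the visit value is 5.5, with no flag.
- SAP 4.2: the visit value is (6.4 + 5.5)/2 = 5.95. The individual value 6.4 meets the HHH limit of > 6.0.
- The child's visit value differs by 5.95 − 5.5 = 0.45. The mean of a cohort of 20 moves by 0.45/20 = 0.02 mmol/L.

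The means barely move; the count is what changes.

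**5. A second gap that the fix must close**

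SAP 4.2 averages several values from the same laboratory in one window. It defines a marked abnormality on any value, but does not say outright that flagging precedes averaging. If the mean were used for flagging, the 5.95 above would not exceed 6.0. Likewise, hemoglobin values of 95 and 112 g/L (assumed) average (95 + 112)/2 = 103.5, hiding a value below the LL limit of 100. Exempting laboratory data from SAP 2.1 is therefore not enough by itself.

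**The case against.** The strongest reply is that SAP 4.2 is the more specific rule and governs. It names unscheduled values and says how to handle several in one window. The ECG section (SAP 4.5) restates the scheduled-visit limit while the laboratory section says the contrary, which looks like a deliberate difference by data type. Read literally, SAP 2.1 would also reach adverse event and medication tables that are not built from visits, so it may be meant only as a convention for by-visit summaries. Output details are also left to a Data Presentation Plan that is not among the documents.

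That is a reasonable reading and probably the intended one. It does not settle the matter: SAP 2.1 is worded to cover every analysis and names its one exception, so a programmer who applies it to laboratory tables is not misreading it.

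It is also fair that the loss is limited and visible. The value stays in the listings, clinically relevant abnormalities must be reported as adverse events (protocol 7.2.4.1), predefined ones trigger central laboratory alerts, and all safety analyses are descriptive. None of this corrects the incidence table. The point about baseline carries less weight, since SAP 2.4 has its own explicit rule and baseline is not itself a summary; naming it in SAP 2.1 only removes doubt.

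Finally, the rule that a central value replaces a local one on the same date can itself hide a marked local value. That is an existing, explicit SAP choice, and the fix below leaves it alone.

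**Conclusion.** The concern holds. SAP 2.1 contradicts both protocol 10.3.5.3 and SAP 4.2 for laboratory data, and no precedence is stated. Following SAP 2.1 can only understate the number of children with a treatment-emergent marked laboratory abnormality, by 5.0 percentage points per affected child in a cohort of 20 and 1.7 points among 60. Those sizes assume that planned enrolment equals the laboratory denominator. How many children would be affected cannot be derived from the documents and may be none. The contradiction is certain from the text; an actual undercount depends on the programmer choosing the general rule over the specific one. It should be fixed before the laboratory tables are produced.

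**What to change.** In SAP 2.1, extend the exception to all laboratory summaries, handled as SAP 4.2 describes, and to the derivation of baseline under SAP 2.4.

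In SAP 4.2, state that marked abnormalities are flagged on each individual central or local value, scheduled or unscheduled, from treatment start to EOT + 3 days. Keep the existing rule that the central value is used when both exist for the same date. As a clarification, state that the window mean is used only for by-visit descriptive summaries.

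The cost is SAP wording and programming; no new data are needed. Compared with outputs built on SAP 2.1, reported abnormality rates may be slightly higher. By-visit means may shift slightly because tests done for cause enter the window mean, as the protocol and SAP 4.2 already provide.

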2.2. Study Analysis Periods

For each dosed participant, the screening, treatment and follow-up phases of the study will be structured as following:

Table 3: Study periods definition

Period	Period Start	Period End
Screening	Starts with the signature of the informed consent form (ICF), may be as early as Day -42	Prior to the administration of the first study treatment dose
Treatment		
Up-Titration	the first dose of study treatment	the participant reaches their iMTD (iMTD for each participant is determined at Week 12, or EOT + 3 days in case of premature treatment discontinuation before Week 12)
Maintenance after Week 12 to 16 (continue treatment at same dose)	Day of Up-Titration end plus 1.	Up to Week 16 or EOT + 3 days in case of premature treatment discontinuation before Week 16

Period	Period Start	Period End
Maintenance after Week 16	Day of Week 16 visit plus 1	EOT (up to 5 years after last participant, first visit)
EOT visit	This visit should be conducted within 1 week of the last dose of study treatment. The participant will then enter the Safety follow-up period.	
Safety follow-up	Day after EOT	EOS - Day of Safety follow-up Phone call (about 30 days after last dose)

In case a participant drops out during a treatment period, the participant will have a Follow-Up period after the last applicable treatment period only if a Follow-Up visit was performed.

Each of these analysis periods is associated with a treatment. Treatments for the Screening and Follow-Up periods are defined as ‘None (screening/follow-up)’, respectively.

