4.1. Adverse Events

Adverse Events and Treatment-Emergent Adverse Events

- Summaries of below adverse event categories will be summarized according to the study periods *Up-Titration*, *Maintenance after Week 12*, *Maintenance after Week 16* as defined in [Table 2](#).
- All reported adverse events with onset following the start of study treatment, or pre-existing conditions that have worsened since baseline, will be defined as treatment-emergent (TEAE) and will be included in the analysis. TEAEs will be recorded up to EOT + 3 days.
- AEs will be analyzed by period, and the start or worsened date-time of the AEs will be used to determine the period the AE falls in.
- For each TEAE, the percentage of participants who have experienced at least 1 occurrence of the given event will be summarized by system organ class, preferred term, and age cohort.
- TEAEs will be tabulated by severity and relationship and will be summarized by system organ class, preferred term, and age cohort.
- Serious AEs and AEs occurring up to EOT + 3 days that lead to death, hospitalization, treatment discontinuation, dose reduction/interruption will be tabulated and listed.
- AEs that occur during screening and that start prior to first dosing will be included in data listings only.
- All reported adverse event terms will be coded with the latest available MedDRA dictionary version.
- COVID-19 related AEs will be listed.

Adverse Events of Special Interest(AESI):

Adverse events of special interest (AESI) for this study have been defined in [Appendix 2](#).

For each AESI category, the percentage of participants who have experienced at least 1 occurrence of the given event will be summarized by system organ class, dictionary derived preferred term, and age cohort.

AESIs will be also tabulated by severity and will be presented by treatment periods, age cohort, body weight and overall. AESIs will also be summarized by relationship to the study drug.

Number of recurrent AESIs will be counted as the total number of occurrences of any TEAEs, i.e., multiple occurrences for the same preferred term for the same participant will be counted multiple times. Average annualized event rate will be calculated as follows:

- 1) Calculate total number of recurrent TEAEs.
- 2) Calculate participant-years of treatment duration (sum of individual participant time-years in a treatment group)
- 3) Average annualized event rate = (total number of recurrent TEAE) / (subject-years of treatment duration)

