AE resolution date	The earlier of the Upper limit and the end of study date	No replacement, considered ongoing at end of study
AE onset date	If the end date of the AE is not before the start of study drug, and if the study drug start falls in the range of possible dates, it is the study drug start date. In all the other cases, it is the lower limit	The earlier of the end date of the AE and the start of study drug
Concomitant medication start date	Lower limit	No replacement, the medication is considered to have started before the study
Concomitant medication end date	The earlier of the Upper limit and the end of treatment date	No replacement, considered ongoing at end of treatment
Death date	Last of the Lower limit and recorded study assessment dates	Last of the recorded study assessment dates

Anomalous information for a date will be handled using the following rules prior to using the imputations mentioned above:

If the day part of a date is non-numeric or has an invalid value, then day will be considered as missing. For example, if date = 44Nov2000 then, as it isn’t possible to have a 44th day of the month, the day will be considered missing.

If the month part of a date does not match that of the possible months, then it will be considered missing, and so will the accompanying day. For example, if date = 21ND99 then both day and month will be considered as missing.

If the year part of a date is non-numeric or has an invalid value, then the whole date will be considered as missing.

General Conventions:

- Study treatments start date is the first day of intake of study treatment. It is derived as the first 'Treatment start date' after sorting in chronological order all records. It coincides with Study Day 1.
- Study treatment end date (EOT) is the last day of intake of study treatment. It is derived as the last 'Treatment end date' after sorting in chronological order all records.
- Starting dose is the dose given on study treatment start date.

Study Day refers to the number of days elapsed since the day of study treatment start, plus 1 (i.e., Study Day 1 is the day of study treatment start). For dates prior to treatment start, it is the negative number of days elapsed between the date under consideration and the day of study treatment start. Therefore, the study day is always different from 0

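### SAP Table 3 ends the last treatment period at EOT instead of EOT + 3 days, so some late treatment-emergent events fall in no by-period table; the SAP death listing is also narrower than the protocol's

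*SAP*

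**What the plan says.** **Periods.** SAP section 2.2, Table 3, divides treatment into three periods. *Up-Titration* is extended to EOT + 3 days if treatment stops before Week 12. The Week 12 to 16 maintenance row ends "Up to Week 16 or EOT + 3 days in case of premature treatment discontinuation before Week 16". *Maintenance after Week 16* ends at "EOT (up to 5 years after last participant, first visit"), with no three-day extension. Safety follow-up begins on the day after EOT and carries no treatment. Below the table, the SAP adds that after a drop-out "the participant will have a Follow-Up period after the last applicable treatment period only if a Follow-Up visit was performed". SAP section 7 fixes the meaning of EOT: "Study treatment end date (EOT) is the last day of intake of study treatment".

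**Adverse events.** SAP 4.1 states: "Summaries of below adverse event categories will be summarized according to the study periods". It names up-titration, maintenance after Week 12 and maintenance after Week 16; follow-up is not among them. It points to Table 2 for the definitions, but Table 2 holds the analysis sets and the periods are in Table 3. Allocation is by date: "the start or worsened date-time of the AEs will be used to determine the period the AE falls in". The treatment-emergent window is wider than the last period: "TEAEs will be recorded up to EOT + 3 days". For events of special interest: "AESIs will be also tabulated by severity and will be presented by treatment periods, age cohort, body weight and overall".

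**Protocol.** Section 10.3.5.1 reports events up to EOT + 3 days, and separately for up-titration and for a maintenance phase that also closes at EOT + 3 days.

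**Deaths.** SAP 4.1 lists fatal AEs occurring up to three days after end of treatment. Protocol 10.3.5.1 asks for a listing of every AE leading to death, and 10.3.5.2 for a listing of every death reported in the study.

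**The concern.** Table 3 applies two rules. Three post-dose days belong to the treatment period for a child who stops before Week 16, but not for one who stops at or after Week 16. The second group is not limited to premature stops: it includes everyone who reaches Week 16, once their treatment ends.

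For these participants, an event with onset on EOT+1 to EOT+3 is treatment-emergent, yet its date places it in follow-up, which the by-period summaries do not report. A participant whose only occurrence of an event falls on those days is counted overall and in no period. The last SAP period then differs in construction from the two before it, and from the protocol's maintenance phase.

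The death listing raises a separate, simpler issue. A reader who expects the complete listing promised in the protocol would receive one cut at EOT + 3 days, and would have to assemble the rest from other outputs.

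**Working it through.** The plan gives no figure to reproduce, so the check applies the rules as written.

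**Inputs.** Period limits: SAP Table 3. EOT = day of last intake: SAP section 7. Allocation by onset date and window to EOT + 3: SAP 4.1. Assumed for illustration: nominal Week 12 = Day 85 and Week 16 = Day 113.

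**Step 1. Where onsets on EOT+1 to EOT+3 fall.**

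| Last dose (EOT) | Onset days | Last treatment period as written | Result |
|---|---|---|---|
| Day 60 | 61–63 | Up-Titration to 60 + 3 = 63 | all three days covered |
| Day 100 | 101–103 | Weeks 12–16 to 100 + 3 = 103 | all three days covered |
| Day 112 | 113–115 | Weeks 12–16 to 112 + 3 = 115 | all three days covered |
| Day 113 | 114–116 | Weeks 12–16 to 113; after Week 16 would run 114 to 113, so it is empty | none covered |
| Day 114 | 115–117 | After Week 16, 114 to 114 | none covered |
| Day 200 | 201–203 | After Week 16, 114 to 200 | none covered |
| Day 700 | 701–703 | After Week 16, 114 to 700 | none covered |

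The break lies exactly at Week 16. Before it, all three days fall in a reported period; from it on, none do.

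**Step 2. The same check with the last period ending at EOT + 3.** A stop on Day 113 gives a last period of 114 to 116, Day 114 gives 114 to 117, Day 200 gives 114 to 203, and Day 700 gives 114 to 703. Every onset then falls in exactly one of the three reported periods, in line with protocol 10.3.5.1.

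**Step 3. Does the sentence under Table 3 close the gap?** It places follow-up after the last applicable treatment period. For a stop before Week 16 this resolves the overlap between a treatment period ending at EOT + 3 and a follow-up starting at EOT + 1. For a later stop the last treatment period itself ends at EOT, so the three days still belong to follow-up.

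**Step 4. Size.** Three onset days per participant stopping at or after Week 16. With about 60 planned participants (SAP 1.2), and if all stop at or after Week 16: 60 × 3 = 180 participant-days at most. This bounds time, not events.

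**Step 5. Death listing.** Follow-up lasts about 30 days and the SAP listing covers the first 3, leaving 30 − 3 = 27 (EOT+4 to EOT+30). Other outputs that should show these deaths:
- The study-discontinuation listing (SAP 3.2), since protocol 5.1.9 counts death as withdrawal from the study.
- The disease-progression listing (SAP 5.2.5), which includes all-cause deaths to EOT + 7 days and so covers EOT+4 to EOT+7, or 4 of the 27 days.
- Possibly the serious-AE listing. The SAP 4.1 sentence can be read as applying the EOT + 3 limit only to the non-serious categories, and protocol 9.2.2 collects SAEs to 30 days after stopping.

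**The case against.** **The gap is an ambiguity, not an omission.** SAP 4.1 says treatment-emergent events enter the analysis and are analysed by period, and the EOT-visit row of Table 3 has participants entering follow-up after a visit held up to a week after the last dose. On that reading the three days might still belong to treatment. This does not carry. The follow-up row of Table 3, the study-period text in SAP 1.2 and the convention in SAP section 7 all tie EOT or the start of follow-up to the last dose. The EOT + 3 window decides whether an event is treatment-emergent; the date rule decides its period. A programmer following Table 3 would reproduce the gap.

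**The harm is easily overstated.** This stands, and three stronger readings should be set aside:
- A reader might infer that aligned windows would make period counts add up to the overall count. They would not. The tables count participants with at least one occurrence, and a participant with the same event in two periods counts in both. The defect is that someone can be counted overall and in no period.
- A reader might want the three days as a percentage of the last period. Any such figure depends on an assumed stopping time, and for a stop on the Week 16 day the period is empty, so no useful upper limit exists.
- A reader might infer that deaths after EOT + 3 days disappear from the report. The outputs named in the working contradict that.

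**The output plan may already cover deaths.** SAP 2.3 leaves the details of outputs to a data presentation plan that is not among the documents. A complete death listing may be specified there, but the SAP text would still fall short of the protocol.

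**Conclusion.** Both points hold as mismatches in the text. For stops at or after Week 16, SAP Table 3 and SAP 4.1 together leave onsets on EOT+1 to EOT+3 out of every by-period AE and AESI table, contrary to the protocol's maintenance window. The tables over the whole treatment-emergent window are unaffected. The dedicated death listing is narrower than protocol 10.3.5.1 and 10.3.5.2 require, although no death data are lost.

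The impact is minor. The study is single-arm, its safety analysis is descriptive, and the affected window is at most about 180 participant-days, assuming 60 participants who all stop at or after Week 16. The number of events in that window cannot be derived from the documents. The Day 85 and Day 113 values are nominal; the break at Week 16 does not depend on them.

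**What to change.** Four wording edits to the SAP:

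1. **Table 3:** for AE analysis, end *Maintenance after Week 16* at EOT + 3 days.
2. **Table 3 or SAP 4.1:** state that, for all participants, onsets up to EOT + 3 days go to the last treatment period and that this takes precedence over Safety follow-up. The design definition of follow-up in SAP 1.2 and protocol 3.1.1 can stay as it is.
3. **SAP 4.1:** change the period cross-reference from Table 2 to Table 3.
4. **SAP 4.1, Deaths:** list all deaths reported up to EOS, with any AE leading to death, and flag those within EOT + 3 days.

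The cost is these edits and minor programming. No protocol change and no new data are needed.
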